### 3.6.1.2 Study Drug Administration Part A

Prior to Day 1, patients will be discontinued from their current anti-TNF medication, other biologic DMARDs or non-biologic DMARDs, except MTX.

The following must be performed on **Baseline (Day 1, Week 0)**:

Review inclusion and exclusion criteria and confirm patient eligibility. If eligible, the following procedures should be performed:

- Physical examination and vital signs;
- Neurological examination;
- Documentation of concomitant medications;
- Assessment of AEs/SAEs/ADRs;
- Urine pregnancy test for applicable female;
- Randomization to one of the study drugs;
- Contact IXRS.

The following efficacy assessments will be performed:

- Patient's assessment: global VAS and HAQ-DI, including patient's pain VAS;
- Physician's assessment: global VAS;
- Joint assessment. Each of the 66/68 joints will be evaluated for tenderness and swelling.

The following laboratory assessments will be performed:

- Clinical chemistry, hematology, urinalysis and HBV DNA only when negative HBsAg and positive HbcAb at screening;
- CRP, ESR;
- PK and PD sample collection;
- Immunogenicity.

The following must be also performed:

- The first of the two infusions of the study drug, as per IXRS.

The following must be performed on **Day 3 (Week 0)**:

- Physical / Neurological examination;
- Documentation of concomitant medications;
- Assessment of AEs/SAEs/ADRs;
- PK and PD sample collection.

The following must be performed on **Day 8 (Week 1)**:

- Physical / Neurological examination;
- Documentation of concomitant medications;
- Assessment of AEs/SAEs/ADRs;
- PK and PD sample collection;
- Immunogenicity.

The following must be performed on **Day 15 ± 1 day (Week 2)**:

- Physical examination and vital signs;
- Neurological examination;
- Documentation of concomitant medications;
- Assessment of AEs/SAEs/ADRs;
- Urine pregnancy test for applicable female;
- Contact IXRS;
- The second of the two infusions of study drug, as per IXRS;
- Clinical chemistry, hematology, urinalysis
- PK and PD sample collection;

- Immunogenicity.

The following must be performed on **Day 17 ± 1 day (Week 2)**:

- Physical / Neurological examination;
- Documentation of concomitant medications;
- Assessment of AEs/SAEs/ADRs;
- PK and PD sample collection.

The following must be performed on **Day 29 ± 3 days (Week 4)**:

- Physical / Neurological examination;
- Documentation of concomitant medications;
- Assessment of AEs/SAEs/ADRs.

The following laboratory assessments will be performed:

- Clinical chemistry, hematology, urinalysis and HBV DNA only when negative HBsAg and positive HbcAb at screening;
- PK and PD sample collection;
- Immunogenicity.

The following must be performed on **Day 57 ± 3 days (Week 8)**:

- Physical / Neurological examination;
- Documentation of concomitant medications;
- Assessment of AEs/SAEs/ADRs.

The following efficacy assessments will be performed:

- Patient's assessment: global VAS and HAQ-DI, including patient's pain VAS;
- Physician's assessment: global VAS;

- Joint assessment. Each of the 66/68 joints will be evaluated for tenderness and swelling.

The following laboratory assessments will be performed:

- Clinical chemistry, hematology, urinalysis and HBV DNA only when negative HBsAg and positive HbcAb at screening;
- IgG, IgM, IgA;
- CRP, ESR;
- PK and PD sample collection.

The following must be performed on **Day 85 ± 3 days (Week 12)**:

- Physical / Neurological examination;
- Documentation of concomitant medications;
- Assessment of AEs/SAEs/ADRs.

The following laboratory assessments will be performed:

- Clinical chemistry, hematology, urinalysis and HBV DNA only when negative HBsAg and positive HbcAb at screening;
- PK and PD sampling;
- Immunogenicity.

The following must be performed on **Day 113 ± 3 days (Week 16)**:

- Physical / Neurological examination;
- Documentation of concomitant medications;
- Assessment of AEs/SAEs/ADRs.

The following efficacy assessments will be performed:

- Patient's assessment: global VAS and HAQ-DI, including patient's pain VAS;
- Physician's assessment: global VAS;

- Joint assessment. Each of the 66/68 joints will be evaluated for tenderness and swelling.

The following laboratory assessments will be performed:

- Clinical chemistry, hematology, urinalysis and HBV DNA only when negative HBsAg and positive HbcAb at screening;
- IgG, IgM, IgA;
- CRP, ESR;
- PK and PD sample collection;
- Immunogenicity.

The following must be performed on **Day 141 ± 3 days (Week 20)**:

- Physical / Neurological examination;
- Documentation of concomitant medications;
- Assessment of AEs/SAEs/ADRs.

The following laboratory assessments will be performed:

- Clinical chemistry, hematology, urinalysis and HBV DNA only when negative HBsAg and positive HbcAb at screening;
- PK and PD sampling.

To be eligible for the second course of treatment, patients must have an absolute neutrophil count (ANC)  $\geq 1.5 \times 10^3/\mu\text{L}$  and platelet counts  $\geq 75 \times 10^9/\text{L}$  observed at Week 20 (V11). If the ANC value and platelet count are marginally lower, re-testing at an unscheduled visit may be performed at the discretion of the Investigator within the 4-week period between Week 20 and Week 24. In case Visit 11 is missed, all safety evaluations including ANC value and platelet count must be completed as an unscheduled visit for patient to be eligible for second course of infusion.

Following must be performed in the unscheduled visit in this case:

- Neurological examination;
- Physical examination and vital signs;

- Documentation of concomitant medications;
- Assessment of AEs/SAEs/ADRs;
- Clinical chemistry, hematology, and urinalysis;

### **3.6.1.3 Study Drug Administration Part B**

Patients with an inadequate response (<50% improvement from Baseline in both the swollen and tender joint counts) at Week 24 (Visit 12), will be eligible to receive a further course of two 1,000 mg i.v. infusions, one infusion at Week 24 (Day 1 of second course) and the second infusion at Week 26 (14 days after first dose of second course).

The following must be performed on **Day 169 ± 3 days (Week 24, Day 1 of the Second course of infusion)**:

Following must be performed:

- Physical examination and vital signs;
- Neurological examination;
- Documentation of concomitant medications;
- Assessment of AEs/SAEs/ADRs;
- Urine pregnancy test for applicable females administered the second course of the study drug;

The following efficacy assessments will be performed:

- Patient's assessment: global VAS and HAQ-DI, including patient's pain VAS;
- Physician's assessment: global VAS;
- Joint assessment. Each of the 66/68 joints will be evaluated for tenderness and swelling.

The following laboratory assessments will be performed:

- IgG, IgM, and IgA;

- Clinical chemistry, hematology, urinalysis and HBV DNA only when negative HBsAg and positive HbcAb at screening;
- CRP, ESR;
- PK and PD sampling;
- Immunogenicity.

The following must be also performed:

- Contact IXRS;
- Randomization;
- The first of the two infusions of the study drug (see Section 3.2.1), as per IXRS for eligible patients only.

The following must be performed on **Day 183 ± 3 days (Week 26, Day 15 of the Second course of infusion)**:

- Physical examination and vital signs
- Neurological examination;
- Documentation of concomitant medications;
- Assessment of AEs/SAEs/ADRs;
- Urine pregnancy test for applicable females administered the second course of the study drug;
- Contact IXRS;
- The second of the two infusions of study drug (see Section 3.2.1), as per IXRS, for eligible patients only.

The following assessments will be performed on **Day 253 ± 7 days (Week 36)**:

- Physical / Neurological examination;
- Document concomitant medications;

- Assessment of AEs/SAEs/ADRs.

The following efficacy assessments will be performed:

- Patient's assessment: global VAS and HAQ-DI, including patient's pain VAS;
- Physician's assessment: global VAS;
- Joint assessment. Each of the 66/68 joints will be evaluated for tenderness and swelling.

Laboratory assessments

- Clinical chemistry, hematology, urinalysis and HBV DNA only when negative HBsAg and positive HbcAb at screening;
- IgG, IgM, IgA;
- CRP, ESR;
- PD sampling;
- Immunogenicity.

### **End of Study Visit**

The following assessments will be performed on **Day 365 ± 7 days (Week 52)**:

- Physical examination and vital signs;
- Neurological examination;
- Document concomitant medications;
- Resting 12-ECG;
- Assessment of AEs/SAEs/ADRs;
- Serum pregnancy test for applicable female;
- Contact IXRS.

The following efficacy assessments will be performed:

- Patient's assessment: global VAS and HAQ-DI, including patient's pain VAS;
- Physician's assessment: global VAS;
- Joint assessment. Each of the 66/68 joints will be evaluated for tenderness and swelling.

The following laboratory assessments will be performed:

- Clinical chemistry, hematology, urinalysis and HBV DNA only when negative HBsAg and positive HbcAb at screening;
- IgG, IgM, and IgA;
- CRP, ESR;
- PD sampling;
- Immunogenicity.

### **Unscheduled Visit Assessments**

Patients may attend the clinic for unscheduled visits at any time for additional safety monitoring at the discretion of the Investigator.

## **3.6.2 Efficacy Assessments**

### **3.6.2.1 ACR and DAS28 Score**

The following assessments will be performed at the time points indicated in Table 2 for the purposes of calculating the ACR and DAS28 response scores.

#### **3.6.2.1.1 Joint Assessments**

Wherever possible, the same person should perform the joint assessment throughout the study (i.e., for all patients at each study center). Independent joint assessors (require at least one or more if necessary) will be assigned at each study center. This person will be independent to the rest of the study team in order to minimize any bias that could be introduced as a result of the assessment. Standardized training will be provided and the training records filed.

Each of the 66/68 joints will be evaluated for tenderness and swelling (prior to taking any required analgesic that day if possible). Immobilized or injected joints and prosthetic joints and joints which have undergone surgery within 1 year of the Screening visit will be excluded from the assessments.

The 66/68 Joint Count evaluates 66 joints for swelling and 68 joints for tenderness and pain with movement. Hip joints can be evaluated for tenderness only - but not for swelling.

The 66/68 joint count includes the following joints: the temporomandibular; sternoclavicular; acromioclavicular; shoulder; elbow; wrist; metacarpophalangeal, proximal interphalangeal, and distal interphalangeal joints of the hands; hip; knee; ankle; tarsus; and the metatarsal phalangeal and proximal joints of the feet.

### **3.6.2.1.2 Patient's Global Assessment of Disease Activity**

Patients will mark on a VAS their overall assessment of how their RA has affected them, rating how they are managing from 0 (very well) to 100 (very poor). This is equivalent to the General Health component of the DAS (see Appendix 5).

Patients will sign and date the completed VAS.

Patient-reported outcomes and physician-reported outcomes should be completed independently of each other (to avoid bias of the Investigator or the patient).

### **3.6.2.1.3 Physician's Global Assessment of Disease Activity**

The physician's assessment of the patient's current disease activity will be documented on a VAS, ranging from 'no disease activity' (0) to 'maximum disease activity' (100) (see Appendix 5). Wherever possible, the same physician should perform the assessment for a given patient at every visit.

The physician will sign and date the completed VAS.

Physician-reported outcomes and patient-reported outcomes should be completed independently from each other (to avoid bias of the Investigator or the patient).

### **3.6.2.1.4 Patient's Assessment of Disability**

If the patient is unable to read and/or write, the HAQ-DI can be completed by the patient's representative based on the patient's verbal responses.

The patient's ability to function in daily life will be assessed using the HAQ-DI questionnaire. This is a widely used patient self-report tool which assesses the degree of difficulty the patient has in accomplishing tasks in eight functional areas, over the previous week, taking into account any aids or help required. It consists of eight component sets: (1) dressing and grooming, (2) rising, (3) eating, (4) walking, (5) hygiene, (6) reach, (7) grip and (8) common daily activities (see Appendix 5).

The HAQ-DI questionnaire includes a pain VAS. Patients will mark on a VAS the current level of pain due to their RA, ranging from 0 (no pain) to 100 (severe pain) (see Appendix 5).

Patients will sign and date the completed questionnaire.

### **3.6.2.2 Systemic Inflammation: CRP Level and ESR**

A blood sample for CRP assessment will be collected and analysis will be conducted by a suitably qualified central laboratory using validated methods.

A whole blood sample (2 mL) will be collected for the erythrocyte sedimentation rate (ESR) value to be measured locally by Westergren method.

### **3.6.3 Pharmacokinetic and Pharmacodynamic Assessments**

#### **3.6.3.1 Pharmacokinetic Assessments**

Blood samples for the determination of concentrations of rituximab will be taken for each treatment at the times presented in the schedules of assessments (see Table 2).

Individual venipunctures for each time point may be performed or an indwelling catheter may be used. The exact date/time of the blood sample collection will be recorded in the patient's eCRF.

The blood samples (approximately 5 mL) will be drawn in K2EDTA tubes and processed using instructions provided by designated central laboratory. Serum will be harvested in duplicate samples approximately 2.5 mL respectively including back-up sample.

Determination of serum concentrations of rituximab will be performed by central laboratory using validated analytical methods. Detailed sample collection, labeling, storage, and shipment information will be described in the Laboratory Manual.

#### **3.6.3.2 Pharmacodynamic Assessments**

Blood samples for the determination of CD19+ count will be taken for each treatment at the times presented in the schedules of assessments (see Table 2). The exact date/time of the blood sample collection will be recorded in the patient's eCRF.

The blood samples (approximately 5 mL) will be drawn and processed using instructions provided by the designated laboratory retained by the Sponsor.

The samples will be analyzed for CD19+ count by designated central laboratory using validated analytical methods. Detailed sample collection, labelling, storage, and shipment information will be described in the Laboratory Manual.

### **3.6.4 Immunogenicity Assessments**

Blood samples (approximately 5 to 8 mL) will be taken at the visits shown in (Table 2) to determine the incidence of HACA and neutralizing antibody (using validated analytical methods).

Blood immunogenicity samples will be collected on Day 1 of First course (prior to the start of the first infusion), and on Weeks 1, 2, 4, 12, 16, 24, 36, and 52 with date and time of sampling accurately recorded. Wherever possible immunogenicity blood samples will be taken at the same time as blood is drawn for other analyses to limit repeated venipuncture. Additionally, immunogenicity should be assessed when patients show signs or symptoms of immune-response-related adverse events.

Human anti-chimeric antibody will be detected in serum samples using validated analytical methods. Serum samples in which HACA are detected will be reflexed to a Neutralizing Antibody Assay to evaluate the effect of the HACA on the biological activity of rituximab. Full instructions for collection, labeling, storage, and shipment of samples are provided in the Laboratory Manual.

### **3.6.5 Safety Assessments**

All the safety assessments must be performed as provided in Table 2.

#### **3.6.5.1 Adverse Events**

The details of the assessment of AEs are presented in Section 5.

#### **3.6.5.2 Clinical Laboratory Assessments**

The list of clinical laboratory assessments is provided in Table 3.

**Table 3 Clinical Laboratory Assessments**

Hematology	White blood cell count, red blood cell count, hemoglobin, platelets, absolute neutrophil count
Clinical chemistry (serum)	Creatinine, aspartate transaminase, alanine transaminase (ALT), lactate dehydrogenase, alkaline phosphatase (ALP), total bilirubin, cholesterol, calcium, glucose, gamma glutamyl transferase (GGT), phosphate, hCG
Urinalysis	Glucose, blood, protein, hCG
Virology	Hepatitis C virus antibodies, human immunodeficiency virus, hepatitis B surface antigen, and hepatitis B core antibody (total and immunoglobulin M), HBV DNA
Other	C-reactive protein, rheumatoid factor, erythrocyte sedimentation rate*, QuantiFERON-TB Gold

\* ESR estimation (Westergren method) and urine pregnancy test would be performed locally

### 3.6.5.3 Physical Examination

A physical examination will be performed by the Investigator and recorded as ‘normal’ or ‘abnormal’ with specified abnormalities at the visits indicated in Table 2. Any persisting abnormalities should be stated each time the examination is performed. Diagnosis of new abnormalities, or worsening of abnormalities, should be recorded as AEs if appropriate.

Wherever possible, the same person should perform the physical examination throughout the study (i.e., for all patients at each study center). The physical examination should include assessment of general appearance, skin, head, neck, throat, lymph nodes, thyroid, abdomen, and cardiovascular, neurological, musculoskeletal/extremities, and respiratory systems.

Body weight will also be measured. Height will be measured at Screening (Visit 1) only.

### 3.6.5.4 Vital Signs

Vital signs (blood pressure, pulse rate, respiratory rate, and oral or tympanic body temperature) will be assessed at the visits indicated in Table 2. BP measurements should be performed after the patient has been in a sitting/lying down position for at least 5 minutes

During all infusions of the study drug, vital signs will be assessed at the following time points:

1. Pre-infusion (within 10 minutes prior to the start of the infusion);
2. Start of infusion (within 30 minutes after the start of the infusion);
3. End of infusion (within 10 minutes after the end of the infusion).

Additional readings may be assessed at the discretion of the Investigator in the event of an infusion-related reaction.

The Investigator must assess all vital signs findings at each visit. If the Investigator finds any clinically relevant abnormalities, these should be reported as AEs/SAEs as appropriate.

### **3.6.5.5 Resting 12-lead ECG**

Resting 12-lead ECG data will be collected at Screening (Visit 1) and EOS (see Table 2).

Patients should rest for at least 5 minutes in a supine position before ECG evaluations.

The original ECG traces and variables must be stored in the patients' medical record as source data. The Investigator should evaluate the ECG from a clinical perspective and the result (whether the ECG result is normal or abnormal) should be recorded on the ECG tracing and on the appropriate section of the eCRF.

### **3.6.5.6 Pregnancy Test**

A serum pregnancy test will be performed at Screening and EOS. Urine pregnancy tests will be performed at the different time points indicated in Table 2 to rule out pregnancy in patients of childbearing potential. If a pregnancy test was performed within 4 weeks prior to the relevant time point, it need not be repeated.

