#### **Second Infusion (Day 15 of First Course)**

Patients who experienced infusion-related reactions to the first infusion should receive study drug as per the initial infusion schedule, with the rate of infusion not exceeding half that associated with the prior reactions. If this reduced rate is tolerated for 30 minutes, then the infusion rate may be increased to the next closest rate following the infusion schedule.

Patients who miss the allocated day (Day 15  $\pm$  1 day) for the second infusion (the first infusion will be administered following randomization on Day 1) will be contacted and another visit arranged as soon as practically possible in order to administer study drug. Such cases will be considered protocol deviations (see Section 3.13).

If a patient experiences a new infection or other AE between the Day 1 and Day 15 infusions of any treatment, the Day 15 infusion should be delayed until the infection or AE has completely resolved and the Investigator considers it safe to resume treatment. A maximum delay of 15 days from the scheduled date of the second infusion is permitted. Patients who have a delay of >15 days in receiving the second infusion due to an AE or otherwise will be discontinued from the study treatment.

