  - Patients are willing to receive oral folic or folinic acid or equivalent during the entire study (mandatory co-medication for MTX treatment), according to local standards and availability.
- 5 Men and women of childbearing potential must use highly effective methods of contraception during the course of the treatment period and for at least 12 months after the last infusion of study drug. A man or woman is of childbearing potential if, in the opinion of the investigator, he or she is biologically capable of having children and is sexually active. Examples of highly effective contraception include:
- combined (estrogen and progestogen containing) hormonal contraception associated with inhibition of ovulation :
    - oral
    - intravaginal
    - transdermal
  - progestogen-only hormonal contraception associated with inhibition of ovulation :
    - oral
    - injectable
    - implantable 
  - intrauterine device (IUD) 
  - intrauterine hormone-releasing system (IUS) 
  - bilateral tubal occlusion 
  - vasectomised partner 
  - sexual abstinence 
-  Hormonal contraception may be susceptible to interaction with the study drug, which may reduce the efficacy of the contraception method.
-  Contraception methods that in the context of this guidance are considered to have low user dependency.
-  Vasectomised partner is a highly effective birth control method provided that partner is the sole sexual partner of the study participant and that the vasectomised partner has received medical assessment of the surgical success.
-  In the context of this guidance sexual abstinence is considered a highly effective method only if defined as refraining from heterosexual intercourse during the entire period of risk associated with the

study treatments. The reliability of sexual abstinence needs to be evaluated in relation to the duration of the clinical trial and the preferred and usual lifestyle of the subject.

- 6 Female patients of childbearing potential must have a negative serum pregnancy test at Screening (Visit 1) and a negative urine pregnancy test at each applicable visit thereafter. Females will be considered to be of non-childbearing potential if they fulfill one of the following criteria at Screening:
- Postmenopausal defined as amenorrheic for at least 12 months following cessation of all exogenous treatments

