ADR: Adverse drug reaction; AE: Adverse event; CRP: C-reactive protein; DNA: Deoxyribonucleic acid; ECG: Electrocardiogram; EOS: End-of-Study; ESR: Erythrocyte sedimentation rate; HACA: Human anti-chimeric antibody; HAQ-DI: Health Assessment Questionnaire-Disability Index; HBV: Hepatitis B virus; HbcAb: Hepatitis B core antibody; HBsAg: Hepatitis B surface antigen; HCV: Hepatitis C virus; HIV: Human immunodeficiency virus; Ig: Immunoglobulin; IXRS: Interactive voice/web response system; PCR: Polymerase chain reaction; PK: Pharmacokinetic; PD: Pharmacodynamic; PML: Progressive multifocal leukoencephalopathy; RF: Rheumatoid factor; SAE: Serious adverse event; TB: Tuberculosis; TNF: Tumor necrosis factor; VAS: Visual analogue scale.

- a The total time period for Screening is not to exceed 30 days. However, in case a washout of currently used anti-TNF medication or DMARDs is required or prophylaxis of latent TB is required, the Screening may be extended to allow for this washout, but is not to exceed 60 days. (Refer to Table 6 for examples of washout periods.)
- b Prior to Visit 2, Baseline, patients will be discontinued from their current anti-TNF medication or other biologic and non-biologic DMARDs, except MTX.
- c Exclusion criteria to be re-checked at admission to the study center.
- d The physical examination should include assessment of general appearance, skin, head, neck, throat, lymph nodes, thyroid, abdomen, and cardiovascular, neurological, musculoskeletal/extremities, and respiratory systems. Body weight will be measured. Height will be measured at Screening only.
- e Neurological examination for signs and symptoms of PML.
- f Blood pressure measurement can be performed prior to drug infusion. To be measured after the patient has been in a sitting/lying down position for at least 5 minutes. During all infusions of study drug, vital signs will be assessed at the following time points: pre-infusion (within 10 minutes prior to the start of the infusion); at the start of infusion (within 30 minutes after the start of the infusion); and at the end of infusion (within 10 minutes from the end of the infusion). Additional readings may be taken at the discretion of the Investigator in the event of an infusion-related reaction.

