- g Posterior-anterior and lateral chest X-rays (or chest radiographs in accordance with local requirements) should be obtained and reviewed by the Investigator or designee. If chest radiographs taken within the past 3 months show no clinically significant abnormality, and there are no signs or symptoms suggestive of pulmonary disease that would exclude the patient from the study, then a chest radiograph does not need to be repeated. Chest X-rays may be repeated at any time during the study for suspected TB or chest infection.
- h Patients should rest for at least 5 minutes in a supine position before ECG evaluation.
- i In women of childbearing potential; serum pregnancy test (central laboratory) at Screening and EOS. Urine pregnancy test prior to each dose (first and second courses of treatment).
- j All patients except withdrawn patients will continue to attend visits until Week 52 regardless of the second course infusion to obtain PK / PD, safety, efficacy, and immunogenicity data.
- k Unscheduled visits should be scheduled as per Investigator discretion. Tests will be performed as per Investigator's discretion.
- l Study drug is required to be dispensed at Week 24 and Week 26, based on ANC value and platelet count at Week 20 and both the swollen and tender joint counts assessed at Week 24. If the ANC value and platelet count are marginally lower, re-testing at an unscheduled visit may be performed at the discretion of the Investigator within the 4-week period between Week 20 and Week 24. In case Visit 11 is missed, all safety evaluations including ANC value and platelet count must be completed as an unscheduled visit for patient to be eligible for second course of infusion.

- m SAIT101 or Rituxan® or MabThera® for intravenous infusion. On Days 1 and 15, each patient will receive one course of two 1,000 mg (10 mg/mL) drug infusions. Patients who, at Week 24, have a <50% improvement from Baseline in both the swollen and tender joint counts will be eligible for a further course of two 1,000 mg drug infusions. Eligible patients in the SAIT101 arm will receive the second course of SAIT101 treatment at Week 24 and Week 26. Eligible patients in the MabThera® arm will receive the second course MabThera® treatment at Week 24 and Week 26. Eligible patients in the Rituxan® arm will be randomized in a 1:1 ratio to receive SAIT101 or Rituxan® treatment at Week 24 and Week 26.

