#### **3.6.1.1 Screening Period**

##### **Visit 1 (-30 days and not to exceed 60 days before Day 1)**

Patients must have the ability and willingness to provide written informed consent (prior to any study-specific procedures being performed) and to comply with the requirements of the protocol. All the Screening assessments should be performed within 30 days prior to randomization on Day 1 (Visit 2, Baseline).

However, in patients who require a washout of current anti-TNF medication or other biologic and non-biologic DMARD treatment (except MTX) the Screening period may be extended to allow for the washout required, but will not exceed 60 days. In these patients all Screening assessments must be performed within 30 days prior to randomization with the exception of the informed consent and chest X-ray.

Once the patient has provided written informed consent and meets the inclusion and exclusion criteria (see Section 3.4), the study center will register the patient in the IXRS.

The following must also be performed:

- Document patient's demographic information (including gender, date of birth and, when possible per local regulations, race), and medical and surgical history (including RA history);
- Physical examination, including height (cm) and weight (kg);
- Neurological examination (for signs and symptoms of PML);
- Chest X-ray, unless taken within the previous 3 months;
- Serum pregnancy test;
- Vital signs;
- Document previous and concomitant medications (including vaccination history);
- Resting 12-lead ECG.

The following safety/laboratory assessments will be performed:

- QuantiFERON® TB- Gold test;
- Serology (HBsAg and HBcAb, HBV DNA by PCR [ $<20$  IU/mL or 112 copies/mL], anti-HCV, and HIV test), IgG, IgM, IgA, clinical chemistry, hematology, and urinalysis;
- CRP, ESR;
- RF.

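### The 4-week waiver in Protocol Section 3.6.5.6 conflicts with the rule of a pregnancy test before every infusion: up to two or three of four infusions could go ahead without a new test

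*Protocol*

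**What the plan says.** Four places in the protocol call for the test and mention no waiver:

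- Table 2, footnote i: "Urine pregnancy test prior to each dose (first and second courses of treatment". The table marks the test at Screening, Day 1, Day 15, Week 24, Week 26 and end of study, and in the unscheduled-visit column.
- Section 3.4.2, criterion 6: a negative serum test at Screening and "a negative urine pregnancy test at each applicable visit thereafter".
- Section 3.6.1.2, in both the Day 1 and Day 15 lists: "Urine pregnancy test for applicable female".
- Section 3.6.1.3, in both the Week 24 and Week 26 lists: "Urine pregnancy test for applicable females administered the second course of the study drug".

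Section 3.6.5.6 points to the same Table 2 time points and then adds: "If a pregnancy test was performed within 4 weeks prior to the relevant time point, it need not be repeated". Footnote i does not refer to this sentence, and the sentence does not refer to footnote i.

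**The concern.** A site that tests before every infusion complies with every section. A site that uses the waiver complies with Section 3.6.5.6 but departs from footnote i and the visit lists. With about 70 centers, practice could differ.

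Pregnancy is exclusion criterion 1 and a reason to stop study treatment (Section 3.7.3). The pre-infusion test is how a site applies those rules before giving 1,000 mg of rituximab.

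- **Day 1.** A new test here can prevent any exposure. Table 2, footnote c asks for "Exclusion criteria to be re-checked at admission to the study center", yet under the waiver the pregnancy exclusion could be confirmed on a Screening result up to 28 days old. Criterion 5, as worded, requires contraception during treatment and for 12 months afterwards; it does not name the Screening interval.
- **Day 15 and Week 26.** Less is at stake. Section 1.3.1 gives a half-life of 19 to 22 days, so drug from the infusion 14 days earlier is still present. A test would prevent a further infusion, not exposure as such. The note to criterion 5, that study drug may weaken hormonal contraception, bears on these later visits and not on Day 1.

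**Working it through.** The documents state no figure to reproduce. The check is a count of days.

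**Inputs**
- Waiver limit: 4 weeks = 28 days (Section 3.6.5.6).
- S = days from the Screening test to Day 1, at most 30 (Section 3.6.1.1). When Screening is extended to 60 days, only consent and the chest X-ray may fall outside the 30 days, so the limit on S still holds.
- Planned infusions: Days 1, 15, 169 (Week 24) and 183 (Week 26) (Table 2).
- Second infusion of the first course: "A maximum delay of 15 days from the scheduled date of the second infusion is permitted" (Section 3.2.2), so Day 30 at the latest.

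**Rule.** A test can be skipped if the last test actually done is no more than 28 days old.

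**Age of the available result at each infusion**
- Day 1: the Screening result is S days old, so the test can be skipped if S ≤ 28.
- Day 15, if Day 1 was tested: 15 − 1 = 14 days, so it can be skipped.
- Day 15, if Day 1 was skipped: S + 14 days. S = 14 gives 28 (can be skipped); S = 15 gives 29 (cannot).
- Week 24: at least 169 − 15 = 154 days since the last scheduled test, so it cannot be skipped.
- Week 26: 183 − 169 = 14 days, so it can be skipped. With the ±3-day windows the gap is 8 to 20 days, and the answer is the same.

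**Most tests that can be skipped, both courses received**

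| Screening before Day 1 | Skippable | Which |
|---|---|---|
| up to 14 days | 3 of 4 | Day 1, Day 15, Week 26 |
| 15–28 days | 2 of 4 | Day 1 or Day 15 (not both), and Week 26 |
| 29–30 days | 2 of 4 | Day 15, Week 26 |

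**Variations**
- Applying the visit windows (Day 15 ±1, Week 24 ±3, Week 26 ±3), every combination gives two or three.
- Reading the limit as strictly under 28 days moves the cut-offs by one day and still gives two or three.
- If the site tests on Day 1 regardless, two can still be skipped (Day 15 and Week 26).
- If only the first course is given, one of two tests can be skipped, or both if S ≤ 14.
- If the second infusion is delayed by 14 days (Day 29), a Day 1 result is 28 days old and still serves. If it is delayed by 15 days (Day 30), the result is 29 days old and a new test is needed. The maximum then falls to two for S up to 28, and to one for S of 29 or 30.

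**Where the waiver operates.** Screening is the first study test, and end of study falls 365 − 183 = 182 days after Week 26. Among scheduled tests, the waiver can therefore apply only at infusion visits, exactly where footnote i demands a test.

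**The case against.** The strongest reply is that Section 3.6.5.6 is the section dedicated to this test: it adopts the Table 2 time points and then grants an exception. Since the waiver would otherwise have almost nothing to apply to, the exception looks deliberate, and what is missing is only a cross-reference. Criterion 6 speaks of applicable visits, which can accommodate a waived test. There are other safeguards: women who are pregnant or planning pregnancy are excluded, pregnancy stops treatment, pregnancies are reportable within 24 hours of awareness (Section 5.5), and an investigator may always test. Finally, two or three of four is a maximum, reached only in women who qualify for the second course and at sites that use every waiver.

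Much of this stands. The exception reading is possible, criterion 6 is the weaker support, and the count is a ceiling. But reading the sentence as an exception does not reconcile the texts; it removes most of footnote i. The conflict with footnote i and the four visit lists remains. The other safeguards act on a pregnancy already known or suspected. They do not replace the test meant to find one before dosing.

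**Conclusion.** The concern holds. The protocol gives two incompatible instructions about pregnancy testing before infusion. On the planned schedule, the more permissive one lets up to three of four infusions proceed without a new test when Screening was no more than 14 days before Day 1, and up to two otherwise. Only the Week 24 test is always required.

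These counts assume a woman of childbearing potential who receives both courses, no unscheduled tests, and a site that uses the waiver whenever it can. The documents give neither the distribution of Screening intervals nor the number of women of childbearing potential, so the number affected is unknown. This is a matter of patient safety and uniform conduct. No endpoint or analysis depends on it; SAP Section 16.6 only lists pregnancy test results.

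**What to change.** Delete the last sentence of Protocol Section 3.6.5.6 and put in its place: *A negative urine pregnancy test is required before every infusion, regardless of the date of any earlier test.* Footnote i, criterion 6 and the visit lists can stay as they are. If the sponsor wants to keep a 4-week waiver, it should be limited to time points without an infusion, although no scheduled test would then qualify for it.

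With this change, none of the four infusions can be given without a new test. The cost is a wording change in one section. All four urine tests are already in Table 2 and are done locally (Table 3 footnote), so the added burden is at most three urine tests per woman that a site might otherwise have skipped.
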